Statistical Analysis Plan

Title: Reducing Maternal Depression and Promoting Infant Social-Emotional Health & Development

NCT03464630

Date: 09/18/2016

Analytic Strategy

Constructs. We will use a systematic approach to construct development to create two parent outcomes (mother positive/negative) and one infant outcome (infant social emotional functioning). *For our outcomes of maternal depression, parenting knowledge and stress, we will examine single indicants. To view potential intervention moderating effects, we will attempt to create a maternal contextual risk indicant (e.g., isolation/support, relationship status, conflict, economic hardship); for maternal depression prior to intervention as a potential moderator, we will view depression onset, chronicity, and severity as well as presence of other treatment including medication to examine each of these and their effect on intervention outcomes.* For factor analysis, given appropriate internal consistency and inter-rate reliability, we will examine questionnaire scales and observational codes using factor analytic techniques [99], retaining a 5:1 subject to parameter ratio. Scale factor loadings above .30 and communality estimates above .15 will be confirmed within SEM methodology to produce fit indices to view how each indicant set fits into their specified domain. If satisfactory, unit-weighting of the standardized score for each indicant will be summed. If not, we will select an index variable within each domain to represent the outcome.

Random Sampling/Attrition Analysis. Though mother-infant pairs will be randomly assigned to the intervention, condition differences may exist due to random sampling failures or differential attrition. To address this issue, 2×2 (Group x Attrition Status) MANOVAS will be performed using the baseline assessment for mother, infant and contextual risk variables. The presence of a statistically significant Group main effect would provide evidence that random assignment was not effective in equating groups. A second possible source of nonequivalence is differential attrition by condition. A Group x Attrition Status significant interaction provides evidence of differential attrition between groups. In general, analyses will proceed using an “intent to treat” approach and all participants recruited will be included in subsequent analyses.

Examination of Acute Intervention Effects (Aim 2)

(Aims 2.1 - 2.3) Our post-assessment n, to examine acute intervention effects, is expected to be 150 (75/condition). We will initially view intervention effects on our mother/infant outcomes using a 2 (pre-post) $\times 2$ (MBN intervention group) repeated measure analysis of variance. We will examine the inter-correlations among outcomes and, if significant, will use a MANOVA approach to examining MBN intervention effects. The F test is robust to non-normality if such non-normality is caused by skewness rather than outliers. We will take appropriate measures to reduce outlier influences. **(Aim 2.4)** To examine the relations between mother change (parenting and maternal depression) and infant change, one approach will be to create individual beta estimates for mothers and infant utilizing the polynomial contrast function within MANOVA to produce individual trajectory scores reflecting parent and infant change from pre to post that can then be used in external between-condition covariate analysis. The trajectory scores will be subjected to an analysis of covariance with infant change trajectories as the dependent variable and parent change as the covariate. We will determine whether the parent change covariate is significantly related to the dependent variable (demonstrating that changes in parenting behavior and child functioning covary). We will determine the statistical significance and effect sizes of intervention effects (ignoring the covariate). We will then determine if entering the parent functioning covariate modifies the intervention effect size and statistical significance. If parent change is strongly linked to infant change, then entering the covariate should result in nonsignificant intervention effects. Estimates of covariance-adjusted effect sizes will provide estimates of the proportion of intervention effect size that can be explained by the parenting change variable. We will test for between-group heterogeneity of covariance to determine whether the strength of association between change in parenting and infant functioning differs by intervention group.

Examination of Moderating Influences (Aim 3) Dosage & Skills Acquisition. To evaluate moderating influences on parent and infant behavior our first focus is on how maternal depression prior to intervention (*i.e.*, *chronicity, severity, receipt of psychiatric treatment/medication*) affects MBN intervention dosage (**3.1**); secondly, we are interested in the moderating effect of dosage on mother and infant change (**3.2**). For **3.1**, we will examine a 2 (hi/lo dosage) x 2 (intervention) ANOVA, using maternal depression indicants (*e.g.*, *chronicity*) as the dependent measure. A significant main effect for dosage would indicate that higher levels of maternal depression are found at different dosage levels; it is anticipated that higher depression will be evidenced in the low dosage group. A significant interaction would indicate a higher level of maternal depression is found within a dosage by condition cell. Though we would not anticipate a significant interaction, we will examine if higher levels of depression are associated with low dosage only within the Mom and Baby Net (MBN) intervention group; this could indicate that the skills focus of MBN learning may have been too intense for highly depressed mothers. For **3.2**, examining dosage as a moderating influence on mother and infant change, we will utilize the individual beta-slope estimates reflecting parent and infant change from Aim 2 as the dependent measures in separate 2 (intervention) x 2 (hi/lo dosage) ANOVA designs. We hypothesize a significant interaction term indicating the highest positive change trajectories will be for the intervention mothers with high dosage, when compared to low dosage intervention mothers and Depression and Developmental Awareness (DDAS) mothers regardless of dosage level. If a significant dose-effect relationship exists within the MBN condition, we will determine if an effective dosage level can be identified that is less than the maximum number of intervention sessions offered. **3.3** analysis will examine Pearson correlations between contextual risk and level of maternal depression and a bi-serial correlation for the relation between contextual risk and dosage (hi/lo) to determine if contextual risks are related to both initial levels of depression and subsequent engagement in intervention. To further examine the contextual risk on mother and infant change, we will form a hi/lo risk categorical variable, based on median split, and utilize the same 2 (intervention) x 2 (hi/lo risk). If a main Intervention effect is significant, we would expect MBN mothers and infants, regardless of risk level, to evidence the greatest improvements when compared to DDAS mothers. If significant interaction effects occur, we would expect mothers and infants within the MBN condition with lower levels of risk to evidence the greatest improvement in functioning and, though not statistically significant, that MBN mothers and infants, even in the presence of high risk, would evidence higher positive change trajectories than those of DDAS mothers and infants.

Maintenance of Effects (Aim 4)

Maintenance affects will be viewed by single indicants for maternal and infant functioning. We estimate that our maintenance sample will be at a minimum n=150 (overall 17% attrition). For this aim, we will examine mother-infant change trajectories utilizing SEM methodology, performing Latent Growth Curve Model (LGCM) analyses, and include an Intervention indicant predicting intercept and slope estimates. This analysis will supplement our Aim 2 analyses and, if the index variables within this analysis generally reflect the acute intervention trajectories (*e.g.*, significant intervention acute effects demonstrate with constructs reflect the same differential pre-post index variable trajectory), will allow us to more strongly view the trajectory of change across time. Given the restricted nature of follow-up assessments, balancing participant burden and desire to maximize assessment completion across time, we will view these maintenance trajectories with caution.

Power Analysis

We expect a pre-post attrition rate of 17% (n=150). For traditional PALS, across a series of randomized control studies, attrition rates ranged from 9% to 24% [26,97]; within our recent Baby-Net R01 study, we evidenced 7% attrition from pre-to- post assessment and 15% at 6-month follow-up working with low-income mothers in KS and OR, some of whom were experiencing elevated levels of depressive symptoms. In this study, a moderate to large effect size ($d=.5 - 1.03$) is anticipated for maternal outcomes and a small to moderate effect size for the infant outcome ($d=.2-.4$ for infants), based on PALS program evidence [18,27], our Baby-Net preliminary results, and evidence of CWDC [100] and Internet-based CBT treatment success [101]. We calculated the smallest effect size to be detected within a 2 x 2 analysis based on .05 alpha, a sample of n=75 per condition and viewed effects relative to a high ($r=.68$) and low ($r=.21$) repeated measures correlation. We found that with power at .95, we could detect an effect as low as $d=.37$ (with low repeated correlation) and $d=.23$ (with high correlation); with power of .80 we could detect an effect size as low as $d=.29$ (with low repeated correlation) and $d=.18$ (with high correlation). Viewing LGCM maintenance trajectories, the number of cases per estimated parameter needs to be sufficient, with a rough guideline of 5:1 [102,103]. Using this guideline, we will have sufficient sample size to estimate 34 parameters within our initial follow-up sample, with 3 time-points and a condition predictor. For our maintenance examination, as noted, we will not statistically view condition differences in trajectories, but rather will hold these examinations to a preliminary view of intervention.

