Assessment Notes/Important Information about the family:

Elevated PHQ9 score? Yes No PHQ9 Total Score: _____

Depression resources provided Crisis Help Card provided

Referral to doctor or home visitor

Assessor/Coach Initials: _____

Risk Identification:

ATQ question #6 endorsed I don't think I can go on

PHQ9 question #9 endorsed Thoughts that I would be better off dead, or of hurting myself

Self-Harm

No plan, no intent to harm self, identifies reasons to not harm self

Lacks clear plan, states would not carry it out, identifies reasons to not harm self*

Has clear plan, means to harm self, cannot identify reasons to stop from harming self*

EMS Called* Participant called GA Crisis Line*

Contacted PI*

Child Abuse/Neglect

RPNI Completed* Safety information provided

Mandated Report Made*

Intimate Partner Violence

EMS called* Safety information provided

Referral to doctor or home visitor

Other Harm _____

Other: _____ **None**

**Must record in AE/SAE Log (on Google docs)*

Consult Needed: Yes No Date/time supervisor was consulted: _____
if you identified any risk above, a consult is needed

Is this a possible AE or SAE? Yes No AE/SAE #: _____

Report of clinical issue being addressed (List each issue one at a time and how it was addressed):

Report of consultation (what information was given to supervisor, what action needs to be taken, how did participant respond, what intervention was implemented, etc.):

Supervisor Comments (follow up steps needed, additional information, etc.):

Assessor/Coach Signature

Date

Supervisor Signature

Date

When complete, scan and email to [name] for filing and circulation to project team

Assessment Data Checklist

ID#: _____

PRE

POST

Date: _____

Before you leave the home:

Sprint signal: Successful Unsuccessful/Ineligible N/A

Questionnaire: Part 1 Part 2 Checked for missing data

Observation data

ASRI: Followed up for any endorsed safety questions

Safety Monitoring Forms (only used for participants with potential safety concerns)

iPhone Customization Questionnaire

Changes in Contact Information _____

Best times for calling to schedule/confirm training visit _____

Initial and date when items are complete: Initials: _____ Date: _____

At the office:

Enter Assessment Information into Access Database (S: drive)

Update Matriculation Table (Google docs)

Assessment Summary & Risk Identification completed and signed

- Email to supervisor if there is a safety concern

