Possible SAEs need to be reviewed immediately by the PI to determine if the event meets criteria for an SAE. If the event is determined to be an SAE a brief report needs to be written immediately and provided to the PI for review. This report needs to be provided to the NICHD project officer within 24 hours of our discovery of the event.

In cases where there appears to be overlap in criteria, such that an event could be classified as either an AE or an SAE, code and respond to it as an SAE.

Adverse Event Definition:

Adverse event (AE): Any unfavorable medical occurrence or change that may present itself during treatment or administration of an intervention and which may or may not have a causal relationship with the intervention.

Our definition of an AE will incorporate such non-medical occurrences as suicidal ideation, exacerbation of psychopathology, minor symptoms of withdrawal, harm to self or others, disclosure of HIV status, disclosure of a crime committed by juvenile, mandatory report of child abuse, change of home placement or guardianship, homelessness (e.g., runaway), incarceration, and other incidents similar in level of adversity.

The events listed in the above definition are not exhaustive. Other events resulting or having the potential to result in similar injury or distress should be recorded in consultation with the clinical supervisor or PI. Further elaboration of the definition is provided below.

1. **Events reflecting significant change in physical health** include illnesses or injury that either:
 - a. Interfere with usual functioning (e.g., absent from school or work); or
 - b. For which the subject receives medical treatment

These events do not include

- a. Pre-existing conditions unless they worsen during the study period
- b. Life-threatening illnesses (see SAE below)

Examples: Flu; Diagnosis of chronic disease; Broken limb; substance withdrawal; increase in frequency or intensity of asthma attacks

2. Events reflecting significant change in mental health include: onset or exacerbation of suicidal ideation/behavior or non-lethal self-harm; onset of disorder; significant worsening of disorder symptoms

These events do not include

- a. Pre-existing mental health conditions unless they worsen during the study period
- b. Behavior change that does not directly reflect on change in mental health
- c. Life-threatening suicide attempts or self-harm (see SAE below)

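### Adverse events defined as worsening are judged at POST without sight of the PRE value, and the SAP plans no by-arm report of worsening, new self-harm flags or AEs/SAEs

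*SAP*

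**What the plan says.** **Definition.** The mental-health part of the Protocol's section V (Adverse Event Guidelines) counts as adverse events: "onset or exacerbation of suicidal ideation/behavior or non-lethal self-harm; onset of disorder; significant worsening of disorder symptoms". Its exclusions include "Pre-existing mental health conditions unless they worsen during the study period". The general definition in that section also names suicidal ideation as an AE. The General Notes require every AE and SAE to be logged and the log to be reviewed weekly. SAEs go to the funder's project officer within 24 hours.

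**Measurement.** PHQ-9 total, PHQ-9 item 9 (flagged at 1–3) and ATQ item 6 (flagged at 3–5) are checked at PRE and again at POST. Section VI (COVID Remote Procedures) gives the same check for both versions of the POST survey, one per arm.

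**Risk form.** The Assessment Summary & Risk Identification form has one line for the score, "Elevated PHQ9 score? Yes No PHQ9 Total Score", and no field for a prior value. Its lowest self-harm box, "No plan, no intent to harm self, identifies reasons to not harm self", lacks the asterisk that marks items for mandatory logging. The form asks whether the event is a possible AE or SAE. It also states that "if you identified any risk above, a consult is needed".

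**SAP.** Under Constructs, maternal depression is an outcome: "For our outcomes of maternal depression, parenting knowledge and stress, we will examine single indicants". Under Aims 2.1–2.3 the test is on arm means: "We will initially view intervention effects on our mother/infant outcomes using a 2 (pre-post" by arm). The same section adds "We will take appropriate measures to reduce outlier influences" without saying what the measures are. Nothing from Analytic Strategy to Power Analysis mentions adverse events, self-harm items or individual deterioration.

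**The concern.** The guideline's terms (onset, exacerbation, worsening) describe change, but whoever completes or reviews the POST form sees a single day. Mothers enter because they screen positive (Recruitment Form: PHQ-9 of at least 10, PHQ-2 of at least 3 or Edinburgh of at least 11). Many may therefore already be elevated at PRE, and an elevated tick at POST cannot separate stable from worse. Nor can a POST self-harm flag separate new from continuing.

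The same pairing is missing from the analysis. Both programs are given to depressed mothers. A report that follows the SAP could say that mean depression fell in each arm and leave unsaid how many mothers in each arm got worse or newly endorsed self-harm, although the data to answer that will have been collected.

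**Working it through.** **1. What the definition needs against what each step shows.**

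- *Definition:* a POST state compared with an earlier state.
- *Remote POST steps:* current PHQ-9 total, elevated yes/no, item 9 and ATQ item 6 on the day. No instruction to look up PRE.
- *Risk form:* one total, same-day flags, no prior value.
- *Decision tree (section IV):* plan, means and protective factors at the time of contact.

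Take 10 as the elevated level, an assumption based on the in-home referral rule at a PHQ-9 of 10 or more. A mother at 12 at PRE and 24 at POST is ticked yes both times. Her 12-point rise does not appear on the form.

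**2. Sample available.** 180 dyads are to be randomised (Protocol, Aim 2), 1:1. The SAP expects 17% attrition: 180 × 0.83 = 149.4, which reproduces its 150, or 75 per arm. About 15 of 90 per arm would have no POST value. The SAP's power figures concern mean effects, so there is no harms figure to reproduce.

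**3. Equal means can hide unequal worsening.** This example is constructed and is not an estimate. The SAP does not name its depression measure; I take it to be the PHQ-9 total.

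- Arm A: all 75 mothers fall 4 points. Mean change −4.0.
- Arm B: 65 fall 6 and 10 rise 9. Mean change (65 × −6 + 10 × 9)/75 = (−390 + 90)/75 = −4.0.
- The arm-by-time estimate is 0, yet 10/75 against 0/75 worsened by 9 points, a difference of 13.3 percentage points.
- Wilson limits are 7.4% to 22.8% for 10/75 and 0 to 4.9% for 0/75. Newcombe 95% CI: lower 0.133 − √[(0.133 − 0.074)² + 0.049²] = 0.057; upper 0.228. That is 5.7 to 22.8 points.

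**4. Item 9 barely moves the total.** It contributes at most 3 of 27 points. If 5% to 20% of an arm newly endorse it (assumed), the mean shifts through that item by between 0.05 × 1 = 0.05 and 0.20 × 3 = 0.60 point. ATQ item 6 is not in the PHQ-9 total.

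**5. Precision of a by-arm count.** The documents give no event rates, so these are assumed. The 95% half-width for a difference at 75 per arm is 1.96 × √[2p(1 − p)/75]:

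- p = 5%: ±7.0 points
- p = 10%: ±9.6 points
- p = 20%: ±12.8 points

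Power for 10% against 20%, two-sided 0.05: the standard error is √(2 × 0.15 × 0.85/75) = 0.0583 under the null and √[(0.09 + 0.16)/75] = 0.0577 under the alternative. Then (0.10 − 1.96 × 0.0583)/0.0577 = −0.25, giving 40% (32% with Fisher's exact test).

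**6. Missing POST.** If 8 of 75 seen are newly flagged (10.7%), the share of all 90 randomised lies between 8/90 = 8.9% and (8 + 15)/90 = 25.6%. The upper bound takes all 15 missing mothers as unflagged at PRE and flagged at POST.

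**The case against.** The manual has more safeguards than the form alone suggests, and they stand. The lowest-risk box of the decision tree covers mothers who show signs of depression but deny self-harm thoughts. Its action is to document the case and email the supervisor, chasing the signature after 24 hours. The in-home steps refer a mother scoring 10 or more to her doctor or home visitor. The remote POST step has the coach ask an elevated mother about contact with a doctor. PRE and POST forms are kept in one participant folder, so a diligent reviewer could compare them. The SAP does compare mean depression by arm, so average worsening would show.

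Four stronger readings are tempting, and the documents do not support them:

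- *A large PHQ-9 rise without self-harm endorsement escapes supervisor review.* The depression-only branch contradicts this. What remains is an inconsistency: the tree's entry line starts from reported thoughts of death or suicide, and the remote after-call steps name consultation only when self-harm is endorsed.
- *Low-level ideation goes unlogged.* The general rule requires every AE to be logged, and suicidal ideation is a named AE. The missing asterisk conflicts with that rule but does not override it.
- *Missing POST data outweigh sampling error.* The 15/90 = 16.7-point range in one arm exceeds the half-width at a 10.7% rate (1.96 × √[2 × 0.107 × 0.893/75] = 9.9 points) but not the full interval width of 19.8.
- *The outlier step will shrink the mothers who worsened.* The SAP does not say what the measures are. This is a reason to show the change distribution before any such step, and no more.

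It is also fair to say that the example in step 3 was built to equalise the means, and that a by-arm count will be imprecise. Neither point supplies the missing count.

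**Conclusion.** The point holds as a gap in AE classification and harms reporting. None of the existing safeguards puts PRE beside POST, and none yields a count by arm. A report that follows the SAP as written will not say how many mothers per arm worsened or newly endorsed self-harm. The documents do not show that distressed mothers go without attention, and the efficacy analysis is not affected.

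Its actual size cannot be known from the documents, because they give no event rates. The constructed example shows only that a null mean comparison is compatible with a 13-point difference in worsening. This is a worthwhile, low-cost improvement. It rests on three assumptions: PHQ-9 total as the depression measure, 10 as the elevated level, and event rates of 5% to 20%.

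**What to change.** 1. **POST risk form.** Print the PRE PHQ-9 total and the PRE item 9 and ATQ item 6 flags beside the POST values. The existing AE/SAE question and consult can then apply the worsening criterion. No clinical threshold or action changes.
2. **SAP.** Add a descriptive harms paragraph, by randomised arm:
   - PRE-to-POST shift tables for item 9 (0 v 1–3) and ATQ item 6 (1–2 v 3–5), each with a column for missing POST.
   - The between-arm difference in newly flagged mothers with a 95% CI.
   - The cumulative distribution of PHQ-9 change before any outlier handling.
   - AE and SAE counts, with events before randomisation listed separately, because the AE window opens at consent.
   - A statement that the questionnaire shifts carry the comparison and AE counts support it.

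**Cost.** One extra line on a form, one SAP paragraph, three tables and a figure; no new data, visits or staff. If the form change comes too late, the shift tables can still be made from stored responses.

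**Limits to state.** Intervals are wide (about ±10 points at a 10% rate), so the comparison is descriptive. The manual sets no cut-off for significant worsening, which stays a judgement. Coach-recorded AEs may be detected unequally, since the call guides differ and mood rating is set up in one arm only. In the remote procedure PRE is taken by the assigned coach after randomisation, so those PRE flags are not strictly baseline.

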Thank you for your interest! I would like to tell you a little more about the project and see if you would be interested in participating and ask you a few questions to see if you are eligible. It will take about 15 – 20 minutes. You can stop the call at any time or tell me if you do not want to answer any questions. Is now a good time?

- If they can't talk now, set up a date and time for you to call again

About the project: *I have a couple of points I'd like to quickly share with you about the Mom & Baby Net project....if you have any questions, feel free to stop me at any time*

- *The purpose of this research project is to test two iPhone-based program for moms who have been feeling down and their babies. We hope to use this information to improve our program in order to help more moms.*
- *Participants in our study will be given an iPhone to access the program during the course of the study. There is no cost to your family for the loan of the iPhone for free data, texting, and phone calls to use while you are participating in the study. Upon completion of the program and assessment visits, participants will be able to keep the iPhone.*
- *Participating in this project will not affect any other services you currently receive.*
- *We have two different programs that provide information to mothers.*

- Both of the programs include 14 sessions with one session to be covered each week. Most moms spend between 40-60 minutes each week using the iPhone to work on the program and you can start and stop as needed. It will save your place. Each mom will be assigned an individual coach who will provide support through a video call each week. The call will involve watching a video that was created during the session. Each call will last about 20-30 minutes.
- Participants will be asked to complete 2 in-home assessments: 1 assessment visit at the beginning of the project and 1 assessment visit at the end. Each assessment visit will last about 1 to 1 ½ hours. If needed, we can split those into multiple visits. At each assessment visit we will make a video of you and your baby playing together and looking at books. We will also complete an online questionnaire that asks questions about you and your baby.
- Once you complete the first assessment, we will schedule one more home visit to give you the iPhone and support you in using it. This visit will last about 1 hour.
- There may be some benefits to mothers who participate in the program.

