1. In Access, change appointment status to NO SHOW, CANCELLED or RESCHEDULED, and contact the participant to reschedule the appointment. Create a new line for any new appointment you book.

Scheduled Appointments							
Mom ID	Type	Date	Appointment Details	Time	Assessor	Status	Check the Completed Assessments
							Q1 Q2 Interactions iPhoneTrain Notes
101	Pre	4/8/2015		9:00 AM	[name]	Scheduled	
*	101					Completed	
						Cancelled	
						Rescheduled	

2. Re-file participant materials in Assessor's designated file/storage area until the new appointment.

DAY OF HOME VISIT

BEFORE ARRIVING

1. Call or text (if approved by mom) 30 minutes – 1 hour ahead of time to let mom know your ETA.
2. Prepare yourself mentally: have a cool, calm, and matter-of-fact affect.
3. Arrive at the participant's home at the scheduled time (call or text mom if an earlier assessment is running late and you will not be arriving on time).

ARRIVE AT HOME

1. **Greeting the participant: Politely introduce yourself and establish small talk to “break the ice”**
 - Avoid controversial or uncomfortable topics (politics, religion, moral issues, etc.)
 - The goal is to **begin building rapport**. Try to get mom talking about herself or her interests (How many kids in the home, how long have you lived in the area, etc.)
2. **Review order of events** with the mother so she knows what to expect during the home visit:
 - *Today we will be checking for wireless signal and spending some time getting to know you through a questionnaire.*
 - *We will go over the consent form and answering any questions you have.*

- You will answer questions using the iPad. You and I will begin looking at questions together on the iPad then if you would prefer to continue on your own, you can.
- We will also make a 10-minute video of you and your baby playing together and looking at books.
- We can do the questionnaire first or the video first, depending on the timing for the baby.
- The last thing we will do is discuss when would be a good time to set up the training visit.
- What questions do you have?

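### The SAP lets the single infant score mix mother-rated scales with observed codes and does not separate raters, so in Aim 2.4 depression change and infant change could be correlated through shared reporting alone

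*SAP*

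**What the plan says.** The Constructs paragraph of the SAP's Analytic Strategy plans two parent outcomes and "one infant outcome (infant social emotional functioning"). For these constructs, "we will examine questionnaire scales and observational codes using factor analytic techniques". The retention rule is statistical: "Scale factor loadings above .30 and communality estimates above .15 will be confirmed within SEM methodology". If fit is satisfactory, "unit-weighting of the standardized score for each indicant will be summed". The fallback is: "If not, we will select an index variable within each domain to represent the outcome". Internal consistency and inter-rater reliability are preconditions. Nothing distinguishes indicants by informant, and no infant analysis restricted to observed behaviour is planned.

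On data sources, the recruitment script (Protocol, section I, Project Overview) tells mothers: "We will also complete an online questionnaire that asks questions about you and your baby". At the assessment visit (Protocol, section II, Arrive at Home) the mother is told: "You will answer questions using the iPad". The observed source is two five-minute recordings of mother and infant, one of free play and one with books.

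The SAP's Aim 2.4 text opens by defining mother change as covering both parenting and maternal depression. It fits an analysis of covariance of infant change on parent change and reads a significant covariate as "demonstrating that changes in parenting behavior and child functioning covary". It then asks whether adding the covariate removes the intervention effect, and treats the reduction as the proportion of that effect explained.

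**The concern.** Depressive symptoms are an entry criterion, a treatment target and, in Aim 2.4, part of the change used to explain infant change. They are reported by the mother. If the infant score also contains her ratings, both sides of the model share an informant. A mother whose mood lifts may rate the same infant more favourably.

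That would give a within-arm correlation between depression change and infant-score change. It does not depend on the arms differing, so the active comparator does not cancel it. If the arms do differ in depression, part of that difference passes into the infant score. Adjusting for depression change would then remove it, which is the pattern the SAP takes as evidence of linked change.

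The retention cut-offs and reliability conditions do not address this. A mother-rated scale can load above .30 and be internally consistent while carrying mood-related error. What is at stake is the reading of Aim 2.4 and, to a lesser degree, Aim 2.2. Aim 3.2 reuses the same infant change scores.

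**Working it through.** **The plan's own figures.** The SAP's Power Analysis uses 75 per condition, alpha .05 and pre-post correlations of .21 and .68. Its detectable effects follow from the group-by-time F test with noncentrality f² × 150 × 2 / (1 − r) and d = 2f:

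- Power .80: d = .289 and .184 (stated .29 and .18).
- Power .95: d = .372 and .237 (stated .37 and .23).

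On this convention d is half the between-arm difference in pre-post change. In units of that difference, the detectable effects at power .80 are 2 × .289 = .58 and 2 × .184 = .37 raw SD.

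**Inputs from the documents.** n = 150; anticipated maternal effect d = .5-1.03; anticipated infant effect d = .2-.4.

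**Assumptions not in the documents.**

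- There is no true infant effect.
- The score is one mother-rated plus one observed indicant, equally weighted and correlated .3.
- The mother-rated indicant shifts by b SD per SD of depression, with b = 0 to .4.
- All measures have the same pre-post correlation.
- For Aim 2.2, the maternal d applies to depression.

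**Formulas.**

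- SD of the sum = √(1 + 1 + 2 × .3) = √2.6 = 1.612.
- Spurious infant d = (maternal d × b) / 1.612.
- Size of the correlation between depression change and infant-score change = b / 1.612.
- Chance that the covariate is significant: Fisher z with standard error 1/√147, two-sided .05.

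| b | spurious d at maternal d = .5 | at maternal d = 1.03 | correlation (size) | covariate significant |
|---|---|---|---|---|
| 0 | 0 | 0 | 0 | 5% |
| .1 | .03 | .06 | .062 | 12% |
| .2 | .06 | .13 | .124 | 33% |
| .3 | .09 | .19 | .186 | 63% |
| .4 | .12 | .26 | .248 | 87% |

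Worked line for b = .3: .3/1.612 = .186; atanh(.186) × √147 = 2.28; P(Z > 1.96 − 2.28) = .63.

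**Simulation check.** This used 4,000 trials per setting, 75 per arm, pre-post correlations of .21 and .68, and b = 0, .2, .3 and .4. The value b = .1 rests on the formula only.

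- Aim 2.4 depression-change covariate significant: 32-34%, 62-63% and 87% at b = .2, .3 and .4; about 5% at b = 0.
- Aim 2.2 group test on the pooled score, b = .2-.4: rejects in 6-16% of trials at maternal d = .5 and in 9-48% at d = 1.03.
- Aim 2.2 group test on the observed-only score: rejects in 4.6-5.6%.

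**If the fallback index is mother-rated.** Nothing dilutes the bias, so spurious d = maternal d × b. At b = .2-.4 this runs from .5 × .2 = .10 to 1.03 × .4 = .41.

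**The case against.** Several objections have force.

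- **Infant indicants not named.** A reader might infer that the infant score does pool maternal ratings with observation. The documents do not show this. The factor-analysis sentence covers all three constructs and assigns no indicant to the infant one, and a questionnaire about mother and baby need not contain a social-emotional scale. This stands.
- **The bias slope is external.** Neither document says that mood affects these ratings, or by how much. At .1 the effect is slight and at zero it vanishes. This stands, and is why the range is shown.
- **Active comparator.** Both programs have 14 weekly sessions, a coach and weekly video calls. Relief common to both arms cancels in Aim 2.2, and the SAP gives d = .5-1.03 for maternal outcomes generally, not for depression against this comparator. This stands for Aim 2.2. It does not touch the within-arm correlation in Aim 2.4.
- **Aim 2.4 wording.** The sentence about covariation, and the later one on proportion explained, name parenting and not depression. A reader might infer that the SAP expressly draws its conclusion from depression change. It does not; depression enters through the opening definition of mother change. The percentages above apply to the depression covariate only, and none was calculated for parenting change.
- **The fit step.** Poor fit could expose indicants that cluster by informant. That protection is partial, because the fallback index may itself be mother-rated. A two-indicant factor modelled alone is underidentified (three moments, four parameters) and gives no fit indices.
- **Observation has limits.** Ten minutes of video is a narrow basis for infant behaviour and development. Observed parenting comes from the same recordings and possibly the same coders. In the remote procedures the assigned coach runs the recording, and the books at post-assessment may differ. A reader might therefore infer too much by ruling that infant benefit counts only if the observed score shows it. That is a debatable trade-off which the documents do not settle.

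**Conclusion.** The point holds as a gap in what the SAP rules out. The plan permits a partly or wholly mother-rated infant score and has no analysis that would separate shared reporting from change in the infant. That a biased score will be used is not established.

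Aim 2.4 with depression change is the more exposed analysis. Under the stated assumptions a false covariation result appears in about 12% to 87% of trials as the slope goes from .1 to .4, and in 5% at zero. Aim 2.2 is less exposed and only if the arms differ in depression. Its spurious d of .03-.26 reaches the bottom of the SAP's anticipated infant range (.2-.4) only near the top of the assumptions: at maternal d = 1.03 the slope must be at least .2 × 1.612 / 1.03 = .31.

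The size rests on an unknown slope and an unlisted set of indicants. The case for acting is that the separating analysis uses data already collected and bears directly on what the trial can say about mother and infant changing together.

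**What to change.** In Constructs, list each infant indicant and its rater. Alongside any pooled construct, form two infant scores: one from the observational codes of the two recorded interactions only, and one from the mother-rated scales only. Run Aims 2.2 and 2.4 on each and report them side by side.

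In the Aim 2.4 text, state that when the covariate is mother-reported, as depression change is, the covariation and proportion-explained statements rest on the observed infant score. A result seen only in the mother-rated score should be labelled as possibly due to shared reporting.

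The cost is SAP wording and a few extra runs of models already planned, with no new data. The downside is that an observed-only score has fewer indicants and may be noisier; that loss has not been quantified.
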